9.7 Safety Analysis

Adverse events will be monitored during the study and the data analyzed with respect to incidence within each parent study treatment group as well as severity and potential relationship of the AEs to IP.

All AEs with a start date before the first open-label dose date, and that are ongoing from a previous study to this Open-label Extension Study, will be listed in the AE data listing and labeled as “Prior Adverse Event.”

Adverse events with an onset date on or after the first dose of drug in this study, or with an onset prior to the first dose of IP that increase in severity on or after the first dose of IP, will be considered treatment emergent. Treatment-emergent AEs will be summarized for the Safety population by system organ class and preferred term and presented in descending order of frequency within each System Organ Class. Serious AEs and AEs leading to discontinuation will be summarized similarly. Adverse events will be summarized by patient years of exposure (PYE).

Associated laboratory parameters such as hepatic profile, renal function, and hematology values will be grouped and presented together. Individual subject values will be listed and values outside of the standard reference range will be flagged. Shift tables will be produced showing the frequency of shifts from baseline to the highest and to the lowest on-study value in and out of the normal range as well as by visit. Changes from Baseline to each visit for each laboratory parameter will also be summarized.

The change from baseline to each visit for each of the vital sign variables will be summarized. Abnormal vital sign values will be flagged and listed.

The change from baseline to each visit for each of the ECG parameters will be summarized. An outlier analysis of ECG results will be conducted.

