3.3 End of Study

The end of study is defined as either the date of the last visit of the last subject to complete the [REDACTED] Safety Follow-up, or the date of receipt of the last data point from the last subject that is required for primary or secondary analysis, as pre-specified in the protocol and is subject to provisions in [Section 3.2](#), whichever is the later date.

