An overdose is any dose of IP given to a subject or taken by a subject that exceeds the dose described in the protocol. Any overdose, with or without associated AEs, must be promptly

reported to the CRO's Medical Monitor or other designated Drug Safety Center. Cases of overdose should be recorded in the overdose eCRF and AEs associated with the overdose should be reported on relevant AE/SAE sections in the eCRF.

10.1.2 *Monitoring of Subjects with Adverse Events and Serious Adverse Events*

Investigators must carefully monitor each subject for AEs. This includes clinical laboratory variables. Assessments must be made of the seriousness, severity, and relationship to the administration of the IP. After the initial AE/SAE report, the Investigator is required to follow up proactively each subject and provide further information to the Sponsor's Drug Safety or designee on the subject's condition. During the study, all AE/SAEs should be followed up to resolution unless the event is considered by the Investigator to be unlikely to resolve due to the subject's underlying disease, or the subject is lost to follow-up. Safety reporting must comply with ICH E6, 4.11.

All AEs will be recorded by the Investigator from the time the subject signs informed consent until the end of Safety Follow-up [REDACTED] as well as those SAEs made known to the Investigator at any time thereafter that are suspected of being related to IP. All SAEs that occur within [REDACTED] days of the last dose of treatment with the IP, whether or not considered related to the IP, must also be reported. Adverse events and SAEs will be recorded on the AE page of the eCRF and in the subject's source documents. Refer to [Section 13](#) for instructions on how to report SAEs to Drug Safety.

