13 REPORTING OF SERIOUS ADVERSE EVENTS

Reporting requirements for SAEs will be managed on behalf of the sponsor by Sponsor's Drug Safety or designee. Full details of the procedures to be adopted will be documented in a safety management plan approved by responsible parties, in brief:

The Investigator will report any SAE that occurs to any subject from the time written informed consent is signed through the last visit. All SAEs that occur within [REDACTED] days of the last dose of treatment with the IP, whether or not considered related to the IP, must also be reported. Any SAE that is ongoing when the subject completes the study or discontinues from the study will be followed by the Investigator until the event has resolved, stabilized, or returned to baseline status.

Any AE considered serious by the Investigator or Sub-Investigator or that meets serious criteria should be reported to Sponsor's Drug Safety or designee using the designated SAE reporting forms and procedures. Data entry must be completed within 24 hours from the time the study site personnel first learned of the event.

The SAE contact information is as follows:

For Celgene Drug Safety contact information, please refer to the Serious Adverse Event Report Form Completion Guidelines or to the Pregnancy Report Form Completion Guidelines.

The initial report should be promptly followed by detailed, written reports, which will include copies of hospital case records, discharge summaries, autopsy reports, and other documents when requested and applicable. For unrelated cases, a full detailed case description may negate the need for additional hospital case records, discharge summaries, etc.

Investigators will be notified by the Sponsor's Drug Safety or designee of all SAEs that require prompt submission to their IRB or IEC. Investigators should provide written documentation of IRB/IEC notification for each report to the CRO. The CRO will ensure that all SAEs are reported to the appropriate regulatory authorities as required. Reporting of SAEs must comply with ICH E6, 4.11.1.

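### Does the missing end to the treatment-emergent window let late, suspected-related SAEs distort the safety rates?

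*Combined protocol and SAP*

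**What the plan says.** Section 9.7 counts as treatment-emergent "Adverse events with an onset date on or after the first dose of drug in this study", together with earlier events that worsen once dosing has begun. It names no last day and sets no condition on relatedness. It adds "Serious AEs and AEs leading to discontinuation will be summarized similarly" and plans exposure-based summaries ("Adverse events will be summarized by patient years of exposure (PYE"). Appendix A spells out the abbreviation, but no section says when exposure ends.

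Collection is set in Section 10.1.2: "All AEs will be recorded by the Investigator from the time the subject signs informed consent until the end of Safety Follow-up" (its length is redacted), "as well as those SAEs made known to the Investigator at any time thereafter that are suspected of being related to IP". The section also requires SAEs within a redacted number of days of last dose to be reported regardless of cause. On where they go: "Adverse events and SAEs will be recorded on the AE page of the eCRF".

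Section 13 says "The Investigator will report any SAE that occurs to any subject from the time written informed consent is signed through the last visit". It repeats the all-cause window after last dose but has no clause for later suspected events. It presents itself as a summary and refers to a safety management plan for the full procedures.

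Section 9 leaves detailed methodology to a SAP, whose text is not in the file.

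**The concern.** Put the Section 9.7 definition and the Section 10.1.2 collection rule together. Up to the end of Safety Follow-up, SAEs are gathered whatever their cause. Later, in general, they reach the database only when someone suspects the drug. An open-ended treatment-emergent rule would pool the two sets. The suspected-related count, and the share of SAEs judged related, would then rise partly because of how the events were found. The late events also have no matching denominator, whether exposure ends at last dose or at the end of Safety Follow-up.

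This deserves a look because long-term safety is in the study objective (Section 2.1) and relationship to IP is one of the planned summaries (Sections 2.2.3 and 9.7). The late period can also be long. Section 3.3 keeps the study open for the last subject ("The end of study is defined as either the date of the last visit of the last subject to complete the" redacted Safety Follow-up, or a later last data point), and Section 3.2 allows 264 weeks of treatment. With follow-up assumed at 30 to 90 days, a subject who stops at week 52 has 264 − 52 − 30/7 = 207.7 down to 264 − 52 − 90/7 = 199.1 weeks left to the planned week 264.

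**Working it through.** The plan gives no event rate or count to reproduce, so the check has two parts: apply the rules as written, then size the effect on assumed inputs.

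**1. The rule.** Let t be SAE onset, S the end of Safety Follow-up and X the end of the all-cause SAE window, all in days after last dose. S and X are redacted, so the values below are assumptions. From Section 10.1.2, an SAE is recorded if t ≤ S, or t ≤ X, or it is suspected. From Section 9.7, every recorded SAE with onset on or after first dose is counted.

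| S, X (assumed) | Onset t | Suspected: counted | Not suspected: counted | Inside exposure to last dose | Inside exposure to end of follow-up |
|---|---|---|---|---|---|
| 30, 30 | 29 | yes | yes | no | yes |
| 30, 30 | 31 | yes | no | no | no |
| 90, 30 | 91 | yes | no | no | no |
| 90, 90 | 91 | yes | no | no | no |
| 30, 90 | 31 | yes | yes | no | no |
| 30, 90 | 91 | yes | no | no | no |

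The asymmetry is real, but it begins at the later of S and X. Pregnancy outcomes are a narrow exception: Sections 12 and 12.1 handle miscarriages, birth defects and early neonatal deaths as SAEs with no relatedness condition.

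**2. Sections 10.1.2 and 13.** Both carry the all-cause window after last dose. They differ in that Section 13 omits the clause on suspected SAEs learned of later. That fits its role as a summary and does not in itself set up a competing rule.

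**3. Effect on the all-SAE rate.** With N SAEs inside the window, k late suspected SAEs and PY person-years, the ratio of rates is [(N + k)/PY] / [N/PY] = 1 + k/N. The denominator cancels, so the relative effect is the same under either exposure reading.

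- Assume 100 subjects, 2.5 years on drug each, N = 50, k = 3.
- Exposure to last dose: PY = 250. Rates per 100 PY: 100 × 50/250 = 20.0 and 100 × 53/250 = 21.2.
- Exposure to the end of a 90-day follow-up: PY = 100 × (2.5 + 90/365.25) = 274.6. Rates: 18.2 and 19.3.
- Ratio in both cases: 53/50 = 1.06.
- With N = 100 and k = 1 to 5: 1.01 to 1.05.

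**4. Effect where counts are small.** With s suspected SAEs inside the window, the suspected share is (s + k)/(N + k).

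- N = 100, s = 5 (5%): 6/101 = 5.9% for k = 1; 10/105 = 9.5% for k = 5.
- N = 100, s = 15 (15%): 16/101 = 15.8% for k = 1; 20/105 = 19.0% for k = 5.
- One late event added to a term with n events: 1 + 1/n = 1.50, 1.20 and 1.10 for n = 2, 5 and 10.

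All of these are zero effects if k = 0. The late period has no scheduled visits and depends on passive reporting, so k may well be small.

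**5. Can the analyst see the late events?** Section 10.2.4 records start and stop dates for every AE and SAE, and the statistical methods in the Protocol Summary list all safety data. Any SAE starting after follow-up can be flagged from data already collected.

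**The case for a change.** The strongest case for a change is that late capture depends on relatedness, which is itself a tabulated variable, so the bias falls on a planned output. With no hypothesis testing, the descriptive tables are the result. Rare late-onset terms are what a long extension is meant to detect, and they are the ones that one extra event moves most. Closing the window would take a sentence and one derived date.

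The literal gap stands: Section 9.7 has no end date and exposure is undefined. The sensitivity of small counts stands too. Neither makes the plan unsound. Setting the last day of a treatment-emergent flag and the exposure denominator is ordinary SAP work, and Section 9 assigns it there. Section 9.7 speaks of events monitored during the study, and Section 10.1 defines an AE as arising in the course of a study. Late suspected SAEs can therefore fairly be read as a reporting duty rather than tabulated data, although sending SAEs to the eCRF page leaves this open.

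The benefit of moving such events out of the main table is also disputable. It gives a cleaner rate, but it takes the late events most suspected of being drug-related out of the most-read table. Keeping them there errs towards overstating risk, which is defensible in a single-arm safety extension.

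**Conclusion.** No change to the plan follows. The treatment-emergent window has a start and no stated end. After the later of Safety Follow-up and the all-cause SAE window, a non-pregnancy SAE is recorded only if suspected, and it then lacks matching person-time if exposure ends at last dose or at the end of Safety Follow-up. This is missing detail that analysts would normally settle in the SAP, using dates the study already collects.

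The effect is zero without late suspected SAEs and 1% to 5% on the all-SAE rate for 1 to 5 such events per 100. It is larger for the suspected share or a single rare term, and always towards overstating risk. No test or decision threshold depends on it.

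This rests on assumed event counts and an assumed follow-up of 30 to 90 days, because the actual lengths are redacted and the documents give no rates. It also rests on the protocol text alone, since the SAP could not be consulted. The difference between Sections 10.1.2 and 13 is one omitted clause in a section that describes itself as a summary.

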9.8 Interim Analysis

Not applicable.

9.9 Other Topics

9.9.1 *Population Pharmacokinetics and Pharmacokinetics- Pharmacodynamics Analyses*

Population PK and PK/PD analyses will be performed using data from Phase 1 through 3 studies. Results will be reported in a separate independent report.

9.9.2 *Data Monitoring Committee*

An independent Data Monitoring Committee (DMC) will be charged with monitoring safety and efficacy data from the study, as well as general aspects of study conduct. The committee will meet periodically during the study to review analyses concerning enrollment, treatment compliance, adherence to follow-up schedule, and safety data, etc. from the study. The DMC may recommend modifying or stopping the study early due to safety concerns based on data reviews.

10 ADVERSE EVENTS

10.1 Monitoring, Recording and Reporting of Adverse Events

An AE is any noxious, unintended, or untoward medical occurrence that may appear or worsen in a subject during the course of a study. It may be a new intercurrent illness, a worsening concomitant illness, an injury, or any concomitant impairment of the subject's health, including laboratory test values (as specified by the criteria in [Section 11](#)), regardless of etiology. Any worsening (ie, any clinically significant adverse change in the frequency or intensity of a preexisting condition) should be considered an AE. A diagnosis or syndrome should be recorded on the AE page of the CRF rather than the individual signs or symptoms of the diagnosis or syndrome.

CD relapse and related symptoms will be monitored as study endpoints. These occurrences will not be recorded as AEs unless they are new or worse than baseline or if they meet the criteria for seriousness.

In order to facilitate reporting of SARS-CoV-2 events that occur during the study, all AEs and SAEs related to SARS CoV-2 should be reported from the time of consent until the final study visit.

In cases of surgical or diagnostic procedures, the condition/illness leading to such a procedure is considered as the AE rather than the procedure itself.

An adverse drug reaction (ADR) is defined as all noxious and unintended responses to a medicinal product related to any dose (ICH E2A, II.A.2).

An unexpected ADR is defined as an adverse reaction, the nature of which is not consistent with the applicable product information (ICH E2A, II.A.3).

Each AE is to be evaluated for duration, severity, seriousness and causal relationship to the IP. The action taken and the outcome must also be recorded.

Abuse, withdrawal, sensitivity or toxicity to an IP should be reported as an AE. Overdose, accidental or intentional, whether or not it is associated with an AE should be reported on the overdose eCRF. See [Section 10.1.1](#) for the definition of overdose. Any sequela of an accidental or intentional overdose of an IP should be reported as an AE on the AE eCRF. If the sequela of an overdose is an SAE, then the sequela must be reported on an SAE Report Form and on the AE eCRF. The overdose resulting in the SAE should be identified as the cause of the event on the SAE Report Form and eCRF but should not be reported as an SAE itself.

10.1.1 *Treatment of Overdose of Investigational Product*

An overdose is any dose of IP given to a subject or taken by a subject that exceeds the dose described in the protocol. Any overdose, with or without associated AEs, must be promptly

reported to the CRO's Medical Monitor or other designated Drug Safety Center. Cases of overdose should be recorded in the overdose eCRF and AEs associated with the overdose should be reported on relevant AE/SAE sections in the eCRF.

10.1.2 *Monitoring of Subjects with Adverse Events and Serious Adverse Events*

Investigators must carefully monitor each subject for AEs. This includes clinical laboratory variables. Assessments must be made of the seriousness, severity, and relationship to the administration of the IP. After the initial AE/SAE report, the Investigator is required to follow up proactively each subject and provide further information to the Sponsor's Drug Safety or designee on the subject's condition. During the study, all AE/SAEs should be followed up to resolution unless the event is considered by the Investigator to be unlikely to resolve due to the subject's underlying disease, or the subject is lost to follow-up. Safety reporting must comply with ICH E6, 4.11.

All AEs will be recorded by the Investigator from the time the subject signs informed consent until the end of Safety Follow-up [REDACTED] as well as those SAEs made known to the Investigator at any time thereafter that are suspected of being related to IP. All SAEs that occur within [REDACTED] days of the last dose of treatment with the IP, whether or not considered related to the IP, must also be reported. Adverse events and SAEs will be recorded on the AE page of the eCRF and in the subject's source documents. Refer to [Section 13](#) for instructions on how to report SAEs to Drug Safety.

10.2 Evaluation of Adverse Events

A qualified Investigator will evaluate all AEs based on seriousness, severity, causality, duration, action taken, and outcome.

[figure not shown]
10.2.1 *Seriousness*

An SAE (experience) or reaction is any untoward medical occurrence that at any dose (ICH E2A, II.B):

- results in death
- is life-threatening

NOTE: The term "life-threatening" in the definition of "serious" refers to an event in which the subject was at risk of death at the time of the event; it does not refer to an event which hypothetically might have caused death if it were more severe.

- requires inpatient hospitalization or prolongation of existing hospitalization
- results in persistent or significant disability/incapacity
- is a congenital abnormality/birth defect

If an AE is considered serious, the AE page/screen of the eCRF must be completed. The SAE Report Form may also need to be completed if required per the applicable reporting process.

For each SAE, the Investigator will provide information on severity, start and stop dates, relationship to the IP, action taken regarding the IP, and outcome.

10.2.2 Severity

For both AEs and SAEs, the Investigator must assess the severity of the event. The severity of the AE will be characterized as “mild, moderate, or severe” according to the following definitions:

10.2.3 *Causality*

The causal relationship between the IP and the AE has to be characterized as Not Suspected or Suspected as defined below.

10.2.4 *Duration*

For both AEs and SAEs, the Investigator will provide a record of the start and stop dates of the event.

10.2.5 *Action Taken*

The decision to temporarily interrupt dosing as a result of an AE or SAE remains the responsibility of the treating physician, which will not be delayed or refused by the Sponsor. Prior to interruption,

the Investigator may contact the Medical Monitor and forward appropriate supporting documents for review and discussion.

The Investigator will report the action taken with IP as a result of an AE or SAE, as applicable (eg, discontinuation, interruption, or dose reduction of IP, as appropriate) and report if concomitant and/or additional treatments were given for the event.

If dosing is interrupted, the Investigator should contact the Medical Monitor to discuss treatment reinitiation ([Section 7.2.1](#)). See [Section 14](#) for permanent discontinuation of IP.

10.2.6 *Outcome*

The Investigator will report the outcome of the event for both AEs and SAEs.

All SAEs that have not resolved upon discontinuation of the subject's participation in the study must be followed until recovered (returned to baseline), recovered with sequelae, or death (due to the SAE).

10.2.7 *Adverse Events of Special Interest*

Potential AEs that may be a consequence of S1P receptor modulation, AESIs, will be monitored during the study.

[REDACTED] The sponsor may request additional medical information concerning the AESIs that are non-serious.

[REDACTED]

[REDACTED]

[REDACTED]

[REDACTED]

[REDACTED]

[REDACTED]

[REDACTED]

11 CLINICAL LABORATORY EVALUATIONS

The central laboratory will analyze clinical laboratory samples. Further details of the procedures to be followed for sample collection, storage, and shipment will be documented in a laboratory manual.

Repeat testing for protocol-required laboratory tests are to be analyzed by the central laboratory. Additional testing may be performed for significant variations in protocol-required tests at the discretion of the Investigator and in consultation with the Medical Monitor or designee, or at the request of the Sponsor. Approval from the Medical Monitor or designee must be obtained if retest is required to be repeated > 2 times and is not already pre-specified in the protocol.

[figure not shown]
11.1 Hematology

Red blood cell count, total and differential white blood cell (WBC) count (basophils, eosinophils, lymphocytes, monocytes, and neutrophils), platelet count, hemoglobin, hematocrit, mean corpuscular volume, mean corpuscular hemoglobin, and mean corpuscular hemoglobin concentration.

11.2 Chemistry

- Full chemistry panel at Day 1 visit: sodium, potassium, chloride, calcium, magnesium, phosphate, blood urea nitrogen, glucose, albumin, alkaline phosphatase, creatinine, alanine aminotransferase (ALT), aspartate aminotransferase (AST), gamma glutamyltransferase (GGT), total bilirubin, conjugated bilirubin, total cholesterol, triglycerides, [REDACTED] and low-density lipoprotein, [REDACTED]
- All other visits: sodium, potassium, chloride, calcium, magnesium, phosphate, blood urea nitrogen, albumin, alkaline phosphatase, creatinine, ALT, AST, GGT, total bilirubin, conjugated bilirubin, [REDACTED]; Total cholesterol, triglycerides, [REDACTED] and low-density lipoprotein will also be included [REDACTED] and at ET/EoT. [REDACTED].

- Urinalysis: Leukocytes, specific gravity, bilirubin, blood, glucose, ketones, pH, protein, and urobilinogen
- The central laboratory will analyze routine blood samples. Details regarding collection of samples, shipment of samples, reporting of results, laboratory reference ranges, and alerting abnormal values will be supplied to the site before site initiation in a study laboratory manual. The results of the analysis will be made available to each site by the central laboratory.
- Investigators will be asked to comment on those abnormalities on the respective laboratory result page, including a notation of the clinical significance of each abnormal finding in the subject's source documents. The laboratory sheets will be filed with the subject's source documents.

